5. AMENDMENTS AND UPDATES

Number	Date	Section of study protocol	Amendment or update	Reason
2.0	03 May 2018	Milestones	Amendment	Shifting of study milestones due to delay of study initiation
3.0	23 Sep 2019	Milestones	Amendment	Extension of recruitment period

6. MILESTONES

Milestone	Planned Date
IRB/IEC approval	Q2 2018 – Q3 2018
Start of data collection (trial data) FPI	Q3 2018
Recruitment Period (LPI)	Q4 2019
Ramadan Month 2019	May 5th, 2019 – June 4th, 2019 ±1-2 days
Ramadan Month 2020	April 23 rd , 2020 – May 23 rd , 2020 ±1-2 days
Interim Progress Report to SFDA (as per the Saudi FDA templates)	Q4 2018, Q2 2019, Q4 2019, Q2 2020, Q4 2020
End of data collection (LPV)	Q4 2020
Final report of study results: CSR preparation	Q2 2021

7. RATIONALE AND BACKGROUND

Around 415 million patients are affected by DM worldwide. DM is considered an epidemic in many countries of the world, and the number of people affected is expected to double over the next decade. [R16-4703] DM is a major leading cause of many complications and diseases such as heart diseases and several types of infections. T2DM is more common than type 1, comprising 90-95% of all DM cases. [R17-3422] Over 5 million people died from DM in 2015 worldwide. In the Middle East and North Africa, around 36 million patients were affected by DM in 2015, a number expected to rise to 72 million patients by 2040. Saudi Arabia has one of the highest prevalence of DM in the world with over 20% of the population affected. [R16-4703]

Empagliflozin is a selective sodium/glucose co-transporter 2 (SGLT2) inhibitors one of the most recent classes of drugs used to treat T2DM. SGLT2 inhibitors promote the renal excretion of glucose and help lower elevated blood glucose levels in patients with T2DM. [P14-06594] In Saudi Arabia, It is indicated for treatment of T2DM as monotherapy or add-on combination therapy. It is used as monotherapy when exercise and diet control alone do not provide glycaemic control in patients for whom use of metformin is considered inappropriate because of intolerance. It is also used in combination with other glucose lowering agents—including insulin—when they do not provide adequate glycaemic control. [R17-3413] Several clinical trials showed the efficacy of Empagliflozin in reducing the blood glucose level. Furthermore, Empagliflozin is a unique drug among all hypoglycaemic agents because it has shown a reduction in major cardiovascular events, which has not been the case with other oral hypoglycaemic agents. Empagliflozin, as other SGLT2 inhibitors, is associated with some adverse reactions such as urinary tract infections and genital infections, especially in females. In addition, rare cases of diabetic ketoacidosis (DKA) have been reported. [P15-03461], [P13-09179], [P15-05613] In parallel to the launch of SGLT2 inhibitors in Saudi Arabia, the Saudi Food and Drug Authority (SFDA) has requested a non-interventional study to further monitor the safety of Empagliflozin in the country, including during the Ramadan period.

The objectives of this study are to assess the risk of ketoacidosis, severe urinary tract infections, volume depletion, and dehydration associated in patients with T2DM initiating Empagliflozin compared to patient initiating a dipeptidyl peptidase-4 (DPP-4) inhibitors over a 12-month period of follow-up, including the month of Ramadan.

8. RESEARCH QUESTION AND OBJECTIVES

8.1 PRIMARY OBJECTIVE

Non-interventional study with new data collection, with the following aims:

Primary outcomes

To estimate the incidence of:

- Ketoacidosis
- Severe urinary tract infections
- Volume depletion
- Dehydration

in T2DM patients initiating Empagliflozin compared with the incidence in T2DM patients initiating Dipeptidyl peptidase-4 (DPP-4) inhibitors.

8.2 SECONDARY OBJECTIVE

To estimate the risk of each primary outcome with respect to the following definition of exposure:

- The Ramadan period

(1st day of Ramadan to 29th day of Ramadan based on the Islamic Hijri calendar)

[figure not shown]

Figure 1: Ramadan period during study follow-up time

9. RESEARCH METHODS

This is a non-interventional study with new data collection.

This study will cover the period between Q3 2018 and Q4 2020. The main goals of this study are to examine the risk of ketoacidosis, severe urinary tract infections, volume depletion, and dehydration associated with the use of Empagliflozin compared to the use of DPP-4 inhibitors in T2DM patients. The study will use an “incident users” design and compare new users of Empagliflozin with new users of DPP-4 inhibitors. The index date will be defined as the date on which each identified new user receives the index prescription for Empagliflozin or DPP-4 inhibitors. The definition of drug exposure for Empagliflozin will be any patient using at least one prescription of Empagliflozin tablets (10 or 25 mg) or fixed-dose combinations with metformin. The comparator group will be comprised of patients with at least one prescription of a DPP-4 inhibitor: sitagliptin, saxagliptin, linagliptin, vildagliptin, alogliptin (and fixed-dose combinations of these drugs with metformin). Each member of the population exposed to Empagliflozin must have at least one prescription for Empagliflozin, with or without other Glucose-lowering Drugs (GLDs,) and no prior prescriptions of a DPP-4 inhibitor or Empagliflozin during the available pre-index period. Each member of the population exposed to a DPP-4 inhibitor must have at least one prescription for a DPP-4 inhibitor, with or without other GLDs, and no prior prescriptions of a DPP-4 inhibitor or Empagliflozin during the available pre-index period.

Follow-up will start the day after the index date and will continue until any of the following conditions are met: date of death or after 12 months of follow-up, or the date during follow-up that specific exclusion criteria are met, the date of the last continuous treatment of the index drug (Empagliflozin or DPP-4 inhibitor) plus a defined grace period (30 days after the end of the last prescription’s days’ supply in main analyses), or the date in which a new treatment episode starts with any of the other index drugs. Patients who discontinue an index drug and then subsequently initiate another index drug will not be allowed to re-enter the study. Patients will be followed-up for 12 months.

This study will be carried out in the manner of successive surveys that the investigator will be asked to successively write in the case report forms (e-CRFs) from each subject who was initially administered the drug following the study start date until the requested number of subjects is reached. Number of recruited patients will be comparable in each group within a given timeframe (i.e. each site will ensure to recruit similar number of patients for each group according to assigned blocks of enrolment).

Prior to initiation of the study, a written contract shall be concluded, and this contract shall be executed among BI OPU, CRO with the head of the site or the investigator with his/her consent.

Patients will be managed according to the local practice guidelines. The choice of treatment will be solely at the discretion of the participating physician. Empagliflozin and the comparator DPP-4 inhibitor will be administered according to the approved labels in Saudi Arabia. [R17-3427] Hence there are no additional risks to patients by participating in this PASS.

9.1 STUDY DESIGN

This is a non-interventional study with new data collection from T2DM patients in Saudi Arabia. The study will use a “new users” design and compare new users of Empagliflozin to new users of DPP-4 inhibitors in T2DM patients. We have chosen DPP-4 inhibitors because they are considered one of the new groups of hypoglycaemic agents, and they are one of the options to treat patients with T2DM as they have similar indications to Empagliflozin.

Number of recruited patients will be comparable in each group within a given timeframe (i.e. each site will ensure to recruit similar number of patients for each group according to assigned blocks of enrolment).

The index date will be defined as the date on which each identified new user receives the index prescription for Empagliflozin or DPP-4 inhibitors. The patients will be followed up for 12 months after the index date.

The incident-user design avoids comparing a population predominantly composed of first-time users of a newly marketed drug such as Empagliflozin with a population of prevalent users of an older drug who may have stayed on the comparator treatment for a longer time and be less susceptible to the events of interest.

Empagliflozin and the comparator DPP-4 inhibitor will be prescribed according to the local label and at the discretion of the treating physician. [R17-3427] Since this is a non-interventional study, the drug will not be supplied by the sponsor. Furthermore, the sponsor will not cover the expenses related to other medications taken by the patient, interventions, procedures, or diagnostic test.

9.2 SETTING

9.2.1 Study sites

A total of 1500 patients will be enrolled at approximately 25 sites in Saudi Arabia. The treating physicians will mainly be general practitioners (GPs) and/or specialists including endocrinologist, diabetologist & internists. Number of recruited patients will be comparable in each group within a given timeframe (i.e. each site will ensure to recruit similar number of patients for each group according to assigned blocks of enrolment).

9.2.2 Study population

Main diagnosis for study entry

- Patients diagnosed with T2DM will be included.

[figure not shown]
Inclusion criteria:

- Patients who have signed Informed consent form.
- The patients will be at least 18 years old at index date, diagnosed with T2DM in Saudi Arabia, and who will initiate Empagliflozin or DPP4 inhibitors treatment according to the local label and at the discretion of the treating physician during the study period, who have not used other SGLT2 or DPP4 inhibitors during the previous 12 months.

Exclusion criteria:

- Known hypersensitivity to Empagliflozin, the comparator DPP-4 inhibitors or any of their excipients
- Patients for whom Empagliflozin or the comparator DPP-4 inhibitor is contraindicated according SFDA approved label
- Patients prescribed fixed-dose combinations of SGLT2 inhibitors with DPP-4 inhibitors will be excluded.
- The same inclusion and exclusion criteria will be applied to the comparator group, which will include new users of DPP-4 inhibitors.

- **Study visits**

* From Visit 1

Figure 2: Study Visits

Baseline Visit

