9.3.2 Exposures

The definition of drug exposure for Empagliflozin will be any patient using at least one prescription of Empagliflozin tablets (10 or 25 mg) or fixed-dose combinations with metformin. For the comparator group, the patients will have at least one prescription of DPP-4 inhibitors. DPP-4 inhibitor users included in this study will be using one of the following approved drugs in Saudi Arabia: Sitagliptin, Saxagliptin, Vildagliptin, Alogliptin, Linagliptin, or fixed-dose combinations of these drugs with metformin. [R17-3427]

Furthermore, each member of the population exposed to Empagliflozin must have at least one prescription for Empagliflozin, with or without other glucose-lowering drugs (GLDs), and have no prior prescriptions of a DPP-4 inhibitor or Empagliflozin during the available pre-index period. Each member of the population exposed to a DPP-4 inhibitor must have at least one prescription for a DPP-4 inhibitor, with or without other GLDs, and no prior prescriptions of a DPP-4 inhibitor or Empagliflozin during the available pre-index period.

Add-on therapy will be allowed after using the exposure of interest as the initial drug for new users. Therefore, using the drug as part of dual therapy or triple therapy will be allowed.

The use of studied medications will be defined on different levels: current use, recent use and discontinuation of the studied drugs. Current use of the index drugs will be defined from the date of prescription of Empagliflozin or DPP-4 inhibitor to the end of supply for that prescription plus a period of 30 days. Recent use will be defined from the end of current use (30 days after end of supply) until 90 days later (which is 120 days after end of supply).

Discontinuation of the index drug will be defined as no further prescription 120 or more days after the end of the last prescription's supply. Patients who discontinue an index drug and then subsequently initiate another index drug will not be allowed to re-enter the study.

Patients switching to or adding Empagliflozin to other antidiabetic medications will be compared to patients switching to or adding comparator treatment on the same background therapy. Identification of a "new-user" design is an appropriate method for studying second-line therapies in chronic conditions.

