4.5 Datasets to be Analyzed

All patients fulfilling all inclusion criteria and none of the exclusion criteria will be evaluated in an Enrolled Set.

Inclusion criteria are:

- diagnosis with T2DM,
- ≥ 18 years of age at index date,
- initiation of EMPAGLIFLOZIN or DPP-4 inhibitor treatment according to the local label and at the discretion of the treating physician,
- signed informed consent form.

Exclusion criteria are:

- use of SGLT2 inhibitors during the previous 12 months,
- known hypersensitivity to EMPAGLIFLOZIN, the comparator DPP-4 inhibitors or any of their excipients,
- contraindication of EMPAGLIFLOZIN or the comparator DPP-4 inhibitor according SFDA approved label, and
- prescribed fixed-dose combination of SGLT2 inhibitors with DPP-4 inhibitors.

The propensity score analysis will lead to the creation of a Matched Set comprising a subset of subjects in the Enrolled Set (see section 4.9.3). This dataset will be used for additional analysis.

Frequencies of patients included in and excluded from analysis sets will be given.

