4.5.1 Groups and subgroups

Patients are grouped according to the exposure to either EMPAGLIFLOZIN or DPP-4 inhibitors. Data will be analysed per group. DPP-4 inhibitors used include sitagliptin, saxagliptin, linagliptin, vildagliptin, and alogliptin.

Statistical Analysis Plan (SAP)

Document Date: 17APR2019

Document Version: 1.0 Final

All tables will show results per group (EMPAGLIFLOZIN or DPP-4 inhibitors) and for all patients in the analysis set. Additionally, selected tables will show results in subgroups for patients according to their metformin status, namely, whether or not they use metformin fixed combination therapy. Further subgroups are defined by mono, dual or triple therapy with glucose-lowering drugs (GLD) (the treatment complexity status), and by insulin use at baseline (the insulin status).

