4.7.6 Concomitant medication

Concomitant medications are defined as any medication other than Empagliflozin and DPP-4 inhibitors taken during the study. This includes any medication that started prior to enrollment,

Statistical Analysis Plan (SAP)

Document Date: 17APR2019

Document Version: 1.0 Final

but continued during the study, as well as medication that started after enrollment, but continued at the end of study.

Prior medications are defined as any reported medication that started prior to enrollment, whether stopped prior to enrollment or continued.

The prior and concomitant medications reported will be coded using WHO-DD in its 2020 version and summarized by ATC classes.

Frequencies of patients with at least one intake of prior medication, concomitant medication and concomitant medication at index date, respectively, will be presented in summary tables by ATC levels 1, 2 and 4.

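### Only fixed-dose SGLT2/DPP-4 combinations are excluded, so a patient who starts both classes as separate products on the index date is eligible, with comparator exposure or group assignment left unresolved

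*Protocol*

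**What the plan says.** **Concurrent use.** Protocol 9.2.2 states: "Patients prescribed fixed-dose combinations of SGLT2 inhibitors with DPP-4 inhibitors will be excluded". The protocol abstract and SAP 3 say the same, and SAP 4.5 lists as an exclusion "prescribed fixed-dose combination of SGLT2 inhibitors with DPP-4 inhibitors". None of them mentions the two classes taken as separate tablets.

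**Prior use.** Protocol 9.2.2 admits patients "who have not used other SGLT2 or DPP4 inhibitors during the previous 12 months". Protocol 9.3.2 requires "no prior prescriptions of a DPP-4 inhibitor or Empagliflozin during the available pre-index period". SAP 4.5 excludes SGLT2 inhibitor use in the previous 12 months. All of these concern the time before the index date.

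**Other drugs.** A comparator patient "must have at least one prescription for a DPP-4 inhibitor, with or without other GLDs" (Protocol 9.3.2). The same section adds: "Therefore, using the drug as part of dual therapy or triple therapy will be allowed". No drug class is carved out.

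**Grouping.** SAP 4.5.1 says: "Patients are grouped according to the exposure to either EMPAGLIFLOZIN or DPP-4 inhibitors". SAP 4.7.3 likewise describes patients as receiving one or the other.

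**Censoring.** Under Protocol 9 and SAP 3, follow-up starts the day after the index date and ends, among other reasons, when a new episode of another index drug begins. Protocol 9.7.2 names empagliflozin and DPP-4 inhibitors as the index drugs and censors switches during follow-up. Protocol 9.2.2.5 alone also lists other SGLT2 inhibitors as index drugs.

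**The concern.** The fixed-dose exclusion removes patients whose exposure belongs to both arms of the comparison. A patient who takes the same two classes as separate tablets has the same exposure but stays eligible. The criterion turns on tablet form, while the contrast being estimated turns on exposure.

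At stake are the composition of the comparator and the direction of any error. Protocol 7 describes urinary tract infections and genital infections as reactions that empagliflozin shares with other SGLT2 inhibitors, and adds that rare ketoacidosis cases have been reported. If the comparator contains patients taking an SGLT2 inhibitor from the index date, its event rate may rise and the IRR moves toward 1. In a safety study, that is the direction that understates a risk. For patients who meet both cohort definitions, the lack of a rule leaves their placement to be decided during the study or at analysis.

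**Working it through.** No figure in the plan depends on this rule. The study size of 1,500 (750 + 750) is attributed to the regulator, with no event rate or effect size to reproduce. The check is therefore to trace two patients through the rules and then to illustrate the size.

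**Patient A starts a DPP-4 inhibitor and a non-empagliflozin SGLT2 inhibitor as separate products on the index date.**
- Washout (Protocol 9.2.2, SAP 4.5): passed, as there is no earlier use.
- New-user rule (Protocol 9.3.2): passed, as there is no earlier prescription.
- Fixed-dose exclusion: does not apply.
- Cohort: DPP-4, since other glucose-lowering drugs are allowed.
- Censoring: under Protocol 9, Protocol 9.7.2 and SAP 3 the other SGLT2 inhibitor is not an index drug, so it never triggers censoring. Protocol 9.2.2.5 would make it an index drug.

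**Patient B starts empagliflozin and a DPP-4 inhibitor as separate products on the index date.**
- Washout, new-user rule and fixed-dose exclusion: as for patient A.
- Cohort: both definitions in Protocol 9.3.2 are met. SAP 4.5.1 and 4.7.3 assume exclusive exposure and give no assignment rule.
- Censoring: the second drug starts on the index date, before follow-up opens. The rule is written for new episodes or switches during follow-up.

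**Size, for co-users counted in the DPP-4 group.** Let λ be the event rate on a DPP-4 inhibitor alone, Rλ the rate on an SGLT2 inhibitor, and f the share of comparator person-time that is also on an SGLT2 inhibitor. Then

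comparator rate = (1 − f)λ + fRλ

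observed IRR = Rλ / [(1 − f)λ + fRλ] = R / [1 + f(R − 1)]

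R and f are assumptions; the documents give neither. Head-counts are f × 750 and assume equal person-time per patient.

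| f | Patients of 750 | True IRR 3 | True IRR 2 |
|---|---|---|---|
| 1% | about 8 | 3/1.02 = 2.94 | 2/1.01 = 1.98 |
| 5% | about 38 | 3/1.10 = 2.73 | 2/1.05 = 1.90 |
| 10% | 75 | 3/1.20 = 2.50 | 2/1.10 = 1.82 |

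**Scale against sampling error.** Take assumed counts of 15 and 5 events over equal person-time. The IRR is 3, and the standard error of its logarithm is √(1/15 + 1/5) = 0.516. The 95% interval is exp(1.099 ± 1.96 × 0.516), about 1.1 to 8.3. The dilution in the table is small beside that, but it is systematic and avoidable.

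**The case against.** The strongest defence is that the plan treats the two exposures as mutually exclusive. SAP 4.5.1 and 4.7.3 both use either/or language, which supports reading the allowance for other glucose-lowering drugs as not covering the opposite index drug. Sites also recruit into the two groups by assigned enrolment blocks (Protocol 9.2.1), so each patient will have a group in practice. Both points have some force for patient B. They describe an assumption, however, and do not supply an eligibility or assignment rule. They do not touch patient A, whose second drug is not an index drug under Protocol 9 or 9.7.2.

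Three stronger readings are tempting, and the documents do not support them.

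- *A reader might infer that the comparator is generally open to patients already on an SGLT2 inhibitor.* The 12-month washout removes them. The eligibility gap concerns only patients who start both classes, as separate products, on the index date.
- *A reader might infer that the bias always runs toward 1.* That holds only for co-users counted as DPP-4. If patient B is counted as empagliflozin, the comparator is not contaminated.
- *A reader might infer a material distortion.* The documents give no frequency, and at 1% the effect is negligible. The formula also assumes that any SGLT2 inhibitor carries empagliflozin's rate for the outcome concerned.

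Propensity scores cannot be assumed to deal with co-use. The medications named as candidates in SAP 4.9 include neither class.

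**Conclusion.** The concern holds as a narrow gap in eligibility and assignment. Read literally, both documents admit a patient who starts the two classes as separate products on the index date. With another SGLT2 inhibitor, the patient sits in the comparator without being censored for it under Protocol 9, Protocol 9.7.2 and SAP 3. With empagliflozin, the patient has no defined group.

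The direction, toward 1, is conditional on counting such patients as DPP-4. Under the illustrative assumptions a true IRR of 3 falls to between 2.94 and 2.50, and a true IRR of 2 to between 1.98 and 1.82, for f from 1% to 10%. The real f is unknown and may be small. The case for acting rests on the low cost of closing the gap before the Enrolled Set is fixed.

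**What to change.** Define the exclusion by exposure: *any SGLT2 inhibitor together with any DPP-4 inhibitor at the index date, as fixed-dose or separate products*. Use the same wording in the protocol abstract, Protocol 9.2.2, SAP 3 and SAP 4.5.

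For patients already enrolled, apply it when the Enrolled Set is built, and report the number removed per group. Name the data source, because the Visit 1 anti-hyperglycaemic field in Protocol 9.2.2.1 covers agents taken before the baseline visit and may miss a drug first prescribed that day. Suitable sources are:
- the index-drug field at Visit 1;
- the Visit 1 concomitant medication records (Protocol 9.2.2.1, SAP Table 3-1, SAP 4.7.2);
- start dates reported at Visit 2, used only to find products started on the index date.

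Do not use the concomitant medication set of SAP 4.7.6. It is defined as "any medication other than Empagliflozin and DPP-4 inhibitors taken during the study" and so leaves out patient B's second drug.

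Reconcile Protocol 9.2.2.5 with Protocol 9, Protocol 9.7.2 and SAP 3 on whether other SGLT2 inhibitors are index drugs. The new exclusion acts only at the index date, so this is also needed for a consistent as-treated analysis when a comparator patient adds one later.

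The cost is a short edit in four places, one derivation and the loss of the few co-initiators from the analysis. It needs no new visit and no change to treatment.
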